9.0 Provisions to Monitor the Data to Ensure the Safety of Subjects

Adverse events associated with midurethral sling surgery in conjunction with onabotulinumtoxinA injection will be recorded, but only include events such as post-operative urinary retention requiring catheterization, post-operative urinary tract infection, and persistent urinary urgency. Adverse events will be recorded at each follow up visit on Case Report Forms and subsequently will be added in to REDCap electronic data capture system. The PI will be notified of any adverse events, which will be resolved with the patient.

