Women will undergo standardized urologic evaluation at baseline including assessment of urinary symptoms and quality of life using short forms of the Urinary Distress Inventory (UDI-6) and Incontinence Impact Questionnaire (IIQ-7); assessment of overall severity of their incontinence symptoms with the Patient Global Impression of Severity (PGI-S);32 post void residual urine volume; urine analysis and culture; multichannel urodynamic testing; and pelvic exam with prolapse quantification using pelvic organ prolapse quantification system (POP-Q)33. All patients will also complete a 3-day urinary diary at baseline quantifying the number of incontinence episodes (stress and urge). Three months and 1-year after surgery, patients will again complete all baseline measures, including UDI, IIQ, PGI-I, PGI-S, and 3-day diary to report symptom and objective urinary symptoms after treatment. A sample of urine will be obtained for microbiome analysis at each visit.

Scheduled in-person follow-up visits will occur at baseline, 2 and 6-weeks, 3-months, and 1-year after surgery. At the baseline, 3-month, and 1-year visits,

 $PROTOCOL \ TITLE: \ \text{The SLIM Study: } \underline{Sl} \text{ing and Botox} \\ \textcircled{B} \ \underline{Injection for \ \underline{M} ixed \ Urinary \ Incontinence}$

research staff will collect the 3-day diary information and record any adverse events that have occurred during the post-operative period. Subjects will also complete the general and condition specific symptom and QOL questionnaires. In addition, an update of current medication and assessment as to whether any evaluation or treatment for pelvic floor disorders or adverse outcomes from surgery have occurred since the previous evaluation will be assessed by clinical staff at the in-person visits. All patient and survey data will be recorded in RedCAP.

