11.0 Risks to Subjects*

Risks associated with the project are minimal. Patients participating in the project will already be undergoing a retropubic midurethral sling for bothersome stress

 $PROTOCOL \ TITLE: \ \text{The SLIM Study: } \underline{Sl} \text{ing and Botox} \\ \textcircled{M} \ \underline{Injection for } \underline{M} \text{ixed Urinary Incontinence}$

urinary incontinence, and will already have been counseled on and have understood the risks associated with that surgical procedure. None of the risks associated with that surgical procedure will change (increase or decrease) by participating in this study.

This additional risks associated with the procedure are for the patients in the onabotulinumtoxinA arm. Intravesical injection incurs a 5% increased risk of urinary retention requiring clean intermittent self catheterization. All patients will be taught this technique prior to the procedure regardless of study arm. Those with urinary retention have an increased risk of urinary tract infection. This is time-limited and last for less than 2 months on average. All patients will be informed of these risks as part of the consent process.

Another risk to subjects is that we will be collecting their personal health information in a database. All of the data will be kept confidential and will be stored on password protected, secure servers, or in locked cabinet files that only study staff on the project have access to. Personal health information will be stored on files that are separate from the subject's name, all health information will be coded. Coded list will be kept on secure, password protected file.

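### Protocol section 9 appears to restrict recorded adverse events to three urinary types, while section 6 records any event, so other events may be left off the case report form

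*Protocol*

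**What the plan says.** **Protocol section 9 (safety monitoring).** The sentence on scope concerns events associated with the sling together with the injection. It says that these "will be recorded, but only include events such as post-operative urinary retention requiring catheterization, post-operative urinary tract infection, and persistent urinary urgency". On timing and route, "Adverse events will be recorded at each follow up visit on Case Report Forms", after which they go into REDCap. On notification, "The PI will be notified of any adverse events, which will be resolved with the patient".

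**Protocol section 6 (procedures).** The schedule reads: "Scheduled in-person follow-up visits will occur at baseline, 2 and 6-weeks, 3-months, and 1-year after surgery". For data collection, "At the baseline, 3-month, and 1-year visits", "research staff will collect the 3-day diary information and record any adverse events that have occurred during the post-operative period". Separately, whether pelvic floor evaluation or treatment, or "adverse outcomes from surgery have occurred since the previous evaluation will be assessed by clinical staff at the in-person visits".

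**Protocol section 11 (risks).** On the sling operation itself: "None of the risks associated with that surgical procedure will change (increase or decrease) by participating in this study".

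**Protocol section 2 (project abstract).** Physician follow-up is listed at 2 weeks, 3 months and 1 year, with no 6-week visit.

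**SAP.** It does not mention adverse events.

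**The concern.** Sections 6 and 9 give different scopes for the same safety record. Section 6 has no restriction by type. Section 9, where a coordinator would look for the safety rule, names three types, all urinary, after the word *only*.

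The trial adds a drug injection to an operation. Its safety record should therefore be able to show surgical or systemic events as well as retention, infection and urgency. If the narrower rule is followed, such an event could be reported to the PI and dealt with clinically, yet never appear in the data set from which the arms are compared.

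**Working it through.** The plan gives no figure on this point and there is nothing to compute. The check is a comparison of the passages.

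**1. The section 9 sentence alone.** It allows two readings. If *only* governs, the list is closed and holds three types. If *such as* governs, the three are examples, but all are urinary, so it is unclear whether a non-urinary event is of the same kind. The sentence also opens with a limit to events associated with the combined treatment, which section 6 does not have.

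**2. Section 9 against section 6.**

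| Event after surgery | Section 6 | Section 9, closed reading | Section 9, open reading |
|---|---|---|---|
| Retention requiring catheterization, urinary infection, persistent urgency | Recorded | Recorded | Recorded |
| Any other surgical event | Recorded | Not recorded | Unclear |
| Any systemic event | Recorded | Not recorded | Unclear |

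The sections agree on the first row only.

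**3. Whether another passage settles the scope.**

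- Section 9 uses *any* for notifying the PI. Notification is not recording: an event can be notified without being entered on a form.
- Section 6 has clinical staff ask about adverse outcomes from surgery. This helps, but no sentence says that the answers are entered as adverse events.
- Sections 6, 8 and 14 describe general routes for data into the case report forms and REDCap. None defines which adverse events travel by them.
- The available text has no definition of an adverse event, no seriousness criteria, and no rule on which section prevails. The SAP adds nothing.

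The conflict is therefore not resolved elsewhere.

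**4. Consequence for section 11.** Section 11 asserts that participation leaves the surgical risks unchanged. To check this against the trial's data, surgical events of all kinds must be recorded in both arms. A record confined to three urinary types could not support that check; a record on the section 6 scope could.

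**5. Visits.** Section 6 schedules four post-operative visits (2 weeks, 6 weeks, 3 months, 1 year) and names two of them, 3 months and 1 year, for recording by research staff. On the section 2 schedule there are three post-operative visits, and the same two are named. Section 9 requires recording at each follow-up visit. Section 6 does not say that its list is exclusive, so recording at every visit satisfies both sections. This is untidy wording and not a contradiction. The 6-week visit is a real discrepancy between sections 2 and 6.

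**The case against.** The best defence is that staff who obey both sections lose nothing. *Such as* keeps the list open, section 6 tells research staff to record events of any kind, clinical staff ask about surgical outcomes, and the PI hears of every event. Loss requires someone to apply section 9 and ignore section 6. It can also be said that focused capture is a legitimate choice for a product that section 2 describes as a standard treatment for urgency incontinence.

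This defence limits the strength of the point: other events *may* go unrecorded, and a claim that they *will* is not supported. It does not remove the conflict, because nothing tells staff which section to follow. If focused capture was intended, section 6 contradicts it.

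A reader might draw two further inferences, and neither stands.

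- **Early events are missed, or are dated from memory at 3 months.** Section 9 already requires recording at each follow-up visit, so the reading behind this inference is one that the text excludes. Section 8 also allows forms to be completed from source documents as well as self-report. Section 11 gives only an upper bound on an average duration and no time of onset, so the share of events affected cannot be calculated.
- **Participants are told that surgical risk does not change.** Section 11 is protocol text. Its one statement about informing patients follows the retention and infection risks, and the consent pages are not available for review.

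**Conclusion.** The point holds as a conflict of scope between Protocol sections 6 and 9, made worse by a section 9 sentence that both restricts and exemplifies. Three event types are named, all urinary. The number of other events that might be left out cannot be derived from the documents, and nothing shows that any were. The conclusion assumes that at least some staff would take section 9, as the safety section, for the operative rule. The primary PGI-I comparison is not affected. The sponsor should correct this because the safety record is at stake and the change is small. The visit wording is a secondary matter of alignment.

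**What to change.** - **Section 9, scope.** Delete *only* and state that any adverse event is recorded, as section 6 already provides. Keep the three urinary events as named examples. This also lifts the opening limit to associated events as a condition for recording, so the new sentence should make that explicit.
- **Section 6, visits.** Align the list of recording visits with section 9's existing rule that events are recorded at each follow-up visit.
- **Sections 2 and 6, schedule.** Reconcile the two schedules, since the 6-week visit appears only in section 6.

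**Cost.** A few words in the protocol and slightly more data entry at visits already scheduled.

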1.0 Objectives

Primary Aim: To determine whether synthetic retropubic midurethral sling (MUS) combined with concomitant detrusor injections of onabotulinumtoxinA is more effective than midurethral sling alone in improving mixed urinary incontinence (MUI) symptoms.

Secondary Aims:

a. To compare incontinence episode frequency on a 3-day diary in women who undergo midurethral sling plus onabotulinumtoxinA to those who undergo midurethral sling alone.

b. To compare urinary incontinence symptoms and quality of life in women who undergo midurethral sling plus onabotulinumtoxinA to those who undergo midurethral sling alone.

c. To identify baseline factors associated with persistent urgency incontinence in women after midurethral sling alone and midurethral sling plus onabotulinumtoxinA.

Hypotheses:

1. By using a double-blind randomized controlled trial, we will be able to show that retropubic midurethral sling surgery with detrusor muscle onabotulinumtoxinA injection will be more effective at controlling mixed urinary incontinence symptoms than sling surgery alone.

2. Patients who receive both midurethral sling and onabotulinumtoxinA injection will have objectively have fewer incontinence episodes than those who receive midurethral sling alone

3. Patients who receive both treatments will have better quality of life as it relates to urinary symptoms than those who receive midurethral sling alone

4. Patients who have persistent urgency urinary incontinence after either midurethral sling alone or both midurethral sling and onabotulinumtoxinA injection alone will have significantly different baseline urine microbial content than those who do not have persistent urgency symptoms after treatment

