There is no high-quality evidence or consensus amongst specialists on how to approach treatment for women with MUI. The optimal treatment strategy for women with MUI is unclear. Historically, health care providers tried to identify which type of incontinence, stress or urgency, was most bothersome to the patient and treated the bothersome subtype first. Those with stress predominant incontinence underwent surgery, while those with urgency predominant incontinence received medications and behavioral/physical therapy. Currently, the primary surgical treatment of stress incontinence is midurethral slings. Greater than 66% of women undergoing midurethral sling surgery for stress incontinence also report baseline urgency incontinence. Investigators report improvement in urgency incontinence in some women with MUI undergoing midurethral sling, however, subjective outcomes are worse in women with MUI compared to pure stress incontinence and the lower cure rates are associated with persistent urgency incontinence. Studies also demonstrated that urgency incontinence is the major cause of patient dissatisfaction of surgery for stress incontinence and prolapse. Reduced satisfaction and treatment failure after midurethral sling surgery is associated with higher baseline urgency and urgency incontinence. Additionally, one study showed that 33% of women who did not have urgency incontinence symptoms prior to midurethral sling developed urgency symptoms after surgery. This study further complicates the issue, as it is possible that midurethral sling may cause urgency symptoms in some patients. Overall, studies have shown a wide range in improvement of urgency incontinence symptoms after midurethral sling placement between 46-74%. The wide range of anticipated improvement coupled with the not insignificant rate of de novo in urgency incontinence symptoms after midurethral sling, make counseling women with MUI contemplating surgery challenging. Essentially, surgeons can counsel women with MUI that although their stress incontinence symptoms are likely to improve after midurethral sling (90% satisfaction), their urgency incontinence may get better, stay the same, or get worse. Other strategies for treating MUI have also been proposed including treatment with anticholinergic medication in addition to traditional sling surgery. In an AHRQ funded study, anticholinergic medical therapy had minimal to moderate efficacy for treatment of urgency incontinence symptoms. Furthermore, many women taking anticholinergic medications suffer bothersome side effects, such as dry mouth and constipation, and over 50% stop taking the medication during their treatment course. In our prior work, we found that women treated with anticholinergic medications prior to traditional continence surgery were more likely to have urgency symptoms post-operatively, suggesting poorer outcomes in women with MUI. Understandably, patients with persistent urgency symptoms post-operatively are significantly less satisfied with their symptoms and surgical outcomes than patients who have complete resolution of their symptoms.

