
Given the known treatment shortcomings of anticholinergic medications for treatment of urgency incontinences, clinician-investigators began injecting onabotulinumtoxinA into the bladder in an attempt reduce urgency incontinence while minimizing side effects. OnabotulinumtoxinA is a neurotoxin, which inhibits acetylcholine release and temporarily relaxes the bladder muscle to inhibit urgency incontinence. A large NIH funded multicenter double-blind randomized controlled trial investigated the role of detrusor injections with 100 units of onabotulinumtoxinA compared to anticholinergic medications for the treatment of urgency incontinence. More women in the onabotulinumtoxinA group were completely dry (no incontinence episodes) without having the bothersome side effects of the anticholinergic medications. Women in the onabotulinumtoxinA group also had higher rates of transient urinary retention requiring selfcatheterization and urinary tract infection; however, these rates were significantly lower than earlier studies using higher doses of onabotulinumtoxinA. Several studies suggest the optimal dose of onabotulinumtoxinA, which maximized resolution of urinary incontinence while minimizing complications, is 100 units per injection. As a result, onabotulinumtoxinA injections are a standard treatment for urgency incontinence.

Given the superior efficacy and side effect profile of onabotulinumtoxinA and the high rates of persistent urgency incontinence and dissatisfaction after sling surgery in women with MUI, we hypothesize that a combined treatment approach for women with MUI is superior to simply treating the stress incontinence alone. Specifically, women with MUI undergoing sling plus intradetrusor onabotulinumtoxinA will have fewer bothersome incontinence symptoms than women undergoing sling alone. The aim of this double-blind randomized comparative efficacy trial is to determine if women with MUI planning sling surgery sustain greater improvement in their urinary symptoms with the addition of onabotulinumtoxinA injection at the time of sling.

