3.0 Inclusion and Exclusion Criteria

All women with MUI planning surgical intervention with midurethral sling will be approached for study participation. MUI will be defined as an answer of "moderately' or "quite a bit" bothered to Urinary Distress Inventory (UDI) items (2) "urine leakage with a feeling of urgency" AND (3) "urine leakage related to coughing, sneezing, or laughing". $PROTOCOL \ TITLE: \ \text{The SLIM Study: } \underline{Sl} \text{ing and Botox} \\ \textcircled{B} \ \underline{Injection for } \underline{M} \text{ixed Urinary Incontinence}$

Enrolled participants must meet all the following criteria:

- Undergoing mid-urethral sling surgery
- Have symptoms of both stress and urgency urinary incontinence
- Able to consent, fill out study documents, and complete all study procedures and follow-up visits
- At least 18 years of age
- English speaking
- Be able and willing to learn clean intermittent self catheterization technique

Women will be excluded for any of the following reasons:

- History of recurrent UTI (defined as three culture proven UTIs within last 12 months)
- Systemic neuromuscular disease known to affect the lower urinary tract
- Undergoing concomitant prolapse surgery
- Previous incontinence surgery
- Treatment with anticholinergic medication in the last 2 months
 - Darifenacin/Enablex
 - Oxybutynin IR/Ditropan
 - Oxybutynin ER/Ditropan XL
 - Oxybutynin Patch/Oxytrol
 - Oxybutynin Gel/Gelnique
 - Solifenacin/Vesicare
 - Tolterodine IR/Detrol
 - Tolterodine ER/Detrol LA
 - Trospium IR/Sanctura
 - Trospium ER/Sanctura XR
 - Fesoterodine/Toviaz
 - Mirabegron/Myrbetriq
- Previous bladder injection with onabotulinumtoxinA
- Prisoner status
- Pregnancy
- Patients on SGLT2 Inhibitors
 - (canagliflozin, dapagliflozin, and empagliflozin)

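### Protocol section 9.0 lists persistent urinary urgency as an adverse event with no baseline comparison, so non-response is recorded as a harm and true worsening cannot be told apart from it

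*Protocol*

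**What the plan says.** - **Adverse events.** Protocol section 9.0 says that adverse events "will be recorded, but only include events such as post-operative urinary retention requiring catheterization"; the full list is "post-operative urinary retention requiring catheterization, post-operative urinary tract infection, and persistent urinary urgency". Persistent is not defined and no comparison with baseline is given. Events are recorded at each follow-up visit.
- **Entry.** Section 3.0 requires women to "Have symptoms of both stress and urgency urinary incontinence", with at least moderate bother on the UDI item on "urine leakage with a feeling of urgency".
- **Purpose of the injection.** Section 2.0 says that onabotulinumtoxinA "temporarily relaxes the bladder muscle to inhibit urgency incontinence". Section 6.0 says that the primary outcome, the PGI-I, covers both stress and urgency incontinence.
- **Same concept among the aims.** Secondary aim (c) in section 1.0 is "To identify baseline factors associated with persistent urgency incontinence in women after midurethral sling alone and midurethral sling plus onabotulinumtoxinA".
- **Expected harms of the injection.** Section 11.0 says "Intravesical injection incurs a 5% increased risk of urinary retention requiring clean intermittent self catheterization", and that women with retention are more prone to urinary tract infection. Persistent urgency is not among these added risks.
- **Urgency after a sling.** Section 2.0 reports that "studies have shown a wide range in improvement of urgency incontinence symptoms after midurethral sling placement between 46-74" per cent. It also says that continence surgery has made urgency incontinence worse in some women and may bring on urgency in others.
- **Analysis.** Neither Protocol section 8.0 nor the SAP describes how adverse events will be summarised or compared.

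**The concern.** A symptom that every participant brings to the trial, and that the study drug is given to relieve, becomes an adverse event if it is still there afterwards. That is lack of efficacy. The genuine safety question is whether urgency became worse after the sling, with or without the injection, and the listed term cannot answer it because worsened and unchanged urgency carry the same label.

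The direction matters too. Retention and infection are expected more often with onabotulinumtoxinA. Persistent urgency, on the trial's own hypothesis, is expected more often with sling alone. Anyone who later added the listed events together would be setting a benefit against the harms in a figure presented as safety.

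**Working it through.** The plan states no figure on this point, and the sample size is not affected.

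**Step 1. What one record means.** Reading section 9.0 literally against sections 2.0 and 3.0:

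| Urgency after surgery, relative to entry | What it is | Record under section 9.0 |
|---|---|---|
| Gone | Response | None |
| Reduced but present | Partial response | Unclear; arguably an adverse event |
| Unchanged | Non-response | Adverse event |
| Worse | Harm | Adverse event, same label |

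The last two rows cannot be separated from the adverse-event record. This needs no arithmetic.

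**Step 2. What would happen if events were combined.** Neither document plans this, so the following is an illustration.

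Inputs from the documents:
- Retention excess with the injection: 5% (section 11.0), read as percentage points. It refers to retention alone.
- Infection excess: direction only (sections 2.0 and 11.0).
- Persistent urgency on sling alone: 100 - 74 = 26% to 100 - 46 = 54% not improved (section 2.0). This is a rough proxy. The source figure concerns urgency incontinence whereas section 9.0 says urgency, improved women may still have some urgency, and the unimproved include women who became worse.

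Assumptions not in the documents:
- retention 5% on sling alone, so 10% with the injection;
- infection 10% on sling alone, with an excess of 0 to 20 points;
- independent events;
- an injection that either has no effect on persistent urgency or halves it.

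Formula: any event = 1 - (1 - retention)(1 - infection)(1 - persistent urgency).

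Without the urgency item, infection excess 5 points:
- Sling alone: 1 - 0.95 × 0.90 = 14.5%
- With injection: 1 - 0.90 × 0.85 = 23.5%
- Difference: +9.0 points

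With the item, halved from 26% to 13%:
- Sling alone: 1 - 0.95 × 0.90 × 0.74 = 36.7%
- With injection: 1 - 0.90 × 0.85 × 0.87 = 33.4%
- Difference: -3.3 points

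With the item, halved from 54% to 27%: 60.7% against 44.2%, a difference of -16.5 points.

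With the item and no effect (26% in both arms): 36.7% against 43.4%, a difference of +6.7 points.

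Difference in any-event rate (injection minus sling alone, points):

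| Infection excess | Item left out | No effect, 26% v 26% | Halved, 26% v 13% | Halved, 54% v 27% |
|---|---|---|---|---|
| 0 | +4.5 | +3.3 | -7.2 | -19.8 |
| 5 | +9.0 | +6.7 | -3.3 | -16.5 |
| 10 | +13.5 | +10.0 | +0.6 | -13.2 |
| 20 | +22.5 | +16.6 | +8.5 | -6.7 |

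A retention rate of 10% on sling alone gives the same sign in every cell.

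**Step 3. Break-even on a simple count of events.** The count turns in favour of the injection once (persistence on sling alone × relative reduction) exceeds (5 + infection excess).

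| Infection excess | At 26% persistence | At 54% persistence |
|---|---|---|
| 0 | 5/26 = 19% | 5/54 = 9% |
| 5 | 10/26 = 38% | 10/54 = 19% |
| 10 | 15/26 = 58% | 15/54 = 28% |

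**The case against.** The strongest reply is that section 9.0 is a monitoring provision. It says what is written on the CRF and reported to the investigator; it defines no endpoint. A reader might infer that the plan contains a safety comparison already tilted towards onabotulinumtoxinA. The documents do not support that: no any-event rate, pooled count or between-arm safety test appears in either, and reporting each event type by arm would prevent any netting. A reader might also infer that failures are counted twice. Recording a symptom in two places is double counting only if the results are added, and nothing in the plan adds them. Aim (c) looks for predictors of persistence and does not compare arms.

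A reversal of the safety comparison is equally not something the documents establish. It depends on an assumed effect on urgency, assumed base rates and independence, and the table has cells where the difference is only diluted.

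It can also be said that urgency after a sling belongs in safety monitoring, since the Background says that the sling may cause it or make it worse, and that urgency is wider than urgency incontinence. Both are correct. They support recording worsened urgency; they do not support a term that treats an unchanged entry symptom in the same way. The phrase introducing the list could be read as illustrative, so worsening might still be captured, but it would have no distinct label.

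What stands against the point is therefore its consequence and size. The misclassification itself is not answered.

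**Conclusion.** The point holds as a fault in a stated rule. Section 9.0 records non-response as an adverse event and leaves worsened urgency indistinguishable from unchanged urgency. That follows from the text alone.

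The effect on a between-arm comparison is conditional. If the listed events were combined, the item would pull the result towards onabotulinumtoxinA whenever the injection relieves urgency, and would dilute the any-event difference even if it did not. Across the illustrated inputs the result runs from mild dilution (+4.5 to +3.3 points) to clear reversal (+4.5 to -19.8 points). Only the 5-point retention excess and the 46-74% improvement range come from the Protocol; the rest is assumed. No particular size should be quoted as the bias of this trial.

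The primary PGI-I comparison is untouched. The point is worth acting on because the case for adding an injection to a sling rests on benefit and harm being described separately.

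**What to change.** - In Protocol section 9.0, replace persistent urinary urgency with urgency or urgency incontinence that is worse than the woman's own pre-operative baseline.
- Judge this by one worse-than-baseline question on the adverse-event CRF at every follow-up visit, supported at 3 months and 1 year by the UDI urgency item. The 3-day diary cannot serve as the criterion: section 6.0 collects it at baseline, 3 months and 1 year but not at 2 or 6 weeks, and it records leakage episodes, which are not the same as urgency. The UDI item should only support the question, because a woman who enters at the top of its scale cannot score worse.
- In the SAP, report unchanged urgency by arm as an efficacy outcome. Report retention, urinary tract infection and worsened urgency by arm on separate lines, and make no combined any-event comparison that includes unchanged urgency.

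The cost is one CRF field, a sentence in section 9.0 and a short addition to the SAP. The total adverse-event count will be lower, and the report should say why. No visit or sample-size change is needed.
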